**Measured Outcomes:**

The primary outcomes are feasibility and acceptability of the intervention and research procedures. The exploratory outcomes are changes in psychological and behavioral variables, measured via pre-post intervention surveys, and daily diaries and actigraphy each day for 1-2

weeks before and after the intervention. Daily diaries will include psychological variables and self-reported physical activity (collected at night) and sleep outcomes (collected at morning). Covariates will be extracted from the medical record, including date of SCAD event, pregnancy-associated SCAD, medical and psychiatric comorbidities, cardiac rehab attendance, and hospital readmissions. Please refer to tables 1 and 2 below for details of feasibility and acceptability outcomes (Table 1) and exploratory outcomes (Table 2).

Table 1. PRIMARY OUTCOMES (Aims 1 and 2)	
Feasibility	
Enrollment	≥70% of eligible enroll; <20% ineligible due to each criterion; reasons for ineligibility; reasons for refusal; characteristics of refusers
Retention	≤20% participant attrition
Intervention components	≥70% session attendance; fidelity score ≥70%; ≤20% of sessions missed due to videoconference problems; ≤20% connections dropped during session; number (M≤2.0) and types of videoconference problems
Surveys	≥70% pre-intervention and post-intervention surveys completed; ≥70% daily diaries completed for 7 consecutive days; ≤20% missing data on daily diaries
Actigraphy	≥70% completed 7 consecutive days
Acceptability	
Intervention components	Program satisfaction (M≥7.0), ≥70% plan to use the skills, ≥70% would recommend the program to others ( post-survey ); likes, dislikes, suggestions for program improvement ( exit interview )
Surveys	Ease of survey completion (1=not at all, 10=extremely M≥7.0); level of interference (1=not at all, 10=extremely M≤2.0; post-survey ); experiences, challenges, suggestions for improvement ( exit interview )
Actigraphy	Ease of actigraphy completion (1=not at all, 10=extremely M≥7.0; post-survey ); experiences, challenges, suggestions ( exit interview )

Table 2. EXPLORATORY OUTCOMES (Aim 3)		
Psychological Variables	Measurement	Model Component
Non-judgmental body awareness	Multidimensional Assessment of Interoceptive Awareness	Intervention mechanism
Attention regulation	Cognitive Affective Mindfulness Scale-Revised	Intervention mechanism
Cognitive de-centering	Experiences Questionnaire	Intervention mechanism
Distress tolerance	Distress Tolerance Scale	Intervention mechanism
Interoceptive bias	Body Vigilance Scale	FOR process
Intolerance of uncertainty	Intolerance of Uncertainty Scale	FOR process
FOR severity	Assessment of Survivor Concerns	FOR outcome
Cardiac anxiety	Anxiety sensitivity index 3	FOR outcome
Group cohesiveness	Group Cohesiveness Scale	Moderator
Program satisfaction	Program Satisfaction Survey	Moderator
Behavioral Variables	Measurement	Model Component
Sleep duration	Consensus Sleep Diary; Actigraphy	Health behavior outcome
Sleep efficiency	Consensus Sleep Diary; Actigraphy	Health behavior outcome
Sleep onset latency	Consensus Sleep Diary; Actigraphy	Health behavior outcome
Moderate-vigorous physical activity	Physical Activity Vital Sign; Actigraphy	Health behavior outcome
Total steps	Physical Activity Vital Sign; Actigraphy	Health behavior outcome
Sedentary time	Physical Activity Vital Sign; Actigraphy	Health behavior outcome

*Note.* All self-report measures are validated. Variables will be measured pre-post the 8-week intervention, and via daily diaries and actigraphy collected each day during the 1-2 week period before and after the intervention.

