**SPECIFIC AIMS**

Concisely state the objectives of the study and the hypothesis being tested.

The proposed research study has the following objectives:

**Specific Aim 1:** To explore feasibility and acceptability of UpBeat-MBCT for SCAD survivors and make treatment refinements (2 sequential groups of approx. N=8 survivors/group).

Hypotheses: (1) The intervention will be feasible (enrollment, retention, attendance  $\geq 70\%$ ); and (2) acceptable (satisfaction ratings  $\geq 70\%$ , exit interview themes of satisfaction).

**Specific Aim 2:** To explore feasibility of the research procedures (pre-post intervention surveys, daily diaries, actigraphy use). Hypothesis: Each research procedure will be feasible ( $\geq 70\%$  completion).

**Specific Aim 3 (exploratory):** To explore changes in psychological and behavioral variables and their associations. **3a:** To explore changes in psychological variables. Hypothesis: Participants will report improvements in each UpBeat-MBCT mechanism (non-judgmental body awareness, attention regulation, cognitive de-centering, distress tolerance), FOR process (interoceptive bias, intolerance of uncertainty), and FOR outcome (FOR severity, cardiac anxiety). **3b:** To explore changes in behavioral variables. Hypothesis: Participants will report improvements in sleep and physical activity outcomes. **3c:** To explore associations between changes in psychological and behavioral variables. Hypothesis: Changes in psychological variables will be correlated with changes in behavioral variables.

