## **RESEARCH DESIGN AND METHODS**

Briefly describe study design and anticipated enrollment, i.e., number of subjects to be enrolled by researchers study-wide and by Mass General Brigham researchers. Provide a brief summary of the eligibility criteria (for example, age range, gender, medical condition). Include any local site restrictions, for example, "Enrollment at Mass General Brigham will be limited to adults although the sponsor's protocol is open to both children and adults."

The current study will employ an open pilot trial to determine the initial feasibility and

acceptability of a targeted, virtual UpBeat-MBCT intervention for SCAD survivors. We plan to enroll approximately N=20 participants (approx. n=8 survivors/group, accounting for 20% anticipated lost to follow-up). The UpBeat-MBCT intervention will involve 8 MBCT sessions (approximately 1.5 hours each) delivered via synchronous group videoconference, which combines cognitive-behavioral therapy, mindfulness meditation, and cardiac health behavior promotion. During each session, participants will be taught how to use evidence-based mindfulness skills to reduce fear of recurrence and promote positive health behaviors (and physical activity). We will hold two intervention cohort groups that will be run sequentially. Participants in the intervention will be asked to complete a full survey battery of the measures before and after the intervention, and wear an actigraphy device (e.g., to measure physical activity and sleep patterns) for 7 consecutive days within the 1-2 weeks before and after the intervention. In addition, participants will be asked to complete a daily diary of abbreviated measures for 1-2 weeks before and after the intervention. Upon completion of the intervention, participants will complete an audio- or video-recorded exit interview (approx. 45-60 minutes).

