## Analysis Plan

For Aim 1 and Aim 2 will calculate frequencies and proportions and means and standard deviations (or medians and interquartile ranges if variables are non-normal) to assess feasibility and acceptability outcomes. T-tests or chi-square will be used to compare eligible patients who did and did not enroll, and those who enrolled and dropped out, on demographic and clinical variables. Exit interviews will be audio recorded, transcribed, and iteratively analyzed using

thematic content analysis in NVivo 11. Transcripts will be reviewed by two members of the study team to identify themes and develop a coding framework. Discrepancies in coding will then be resolved through discussion.

For Aim 3, we will examine frequency distributions for each exploratory outcome at each timepoint and use non-parametric tests if needed. We plan to use linear mixed effects models with repeated measures and an unstructured covariance matrix to assess changes over time for each psychological and behavioral variable (separate dependent variables). The predictor variables will be time (fixed effect: up to 16 levels across pre-post intervention surveys and daily diaries or actigraphy) and covariates relevant for each dependent variable (random effects). If there are any time effects, we will conduct follow up analyses to determine if those effects show a change over the course of the intervention period in the expected direction. We will create change scores (post-intervention survey minus pre-intervention survey) and explore correlations of changes in psychological variables with changes in behavioral variables. Missing data will be imputed using maximum likelihood estimation and, as a sensitivity analysis, the last observation carried forward. Given the exploratory nature of the proposed pilot study, we will focus the interpretation of Aim 3 analyses on effect sizes (Cohen's d) rather than statistical significance to assess potential signals for intervention effects.

For studies involving treatment or diagnosis, provide information about standard of care at Mass General Brigham (e.g., BWH, MGH) and indicate how the study procedures differ from standard care. Provide information on available alternative treatments, procedures, or methods of diagnosis.

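### Retention, a primary feasibility benchmark, has two pass marks: at least 70% retained in Aim 1, at least 80% retained in Table 1

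*Combined protocol and SAP*

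**What the plan says.** Specific Aims, Aim 1, hypothesis (1) reads "The intervention will be feasible (enrollment, retention, attendance", followed by one threshold of at least 70% for the three items.

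Measured Outcomes names feasibility and acceptability as the primary outcomes and sends the reader to the tables: "Please refer to tables 1 and 2 below for details of feasibility and acceptability outcomes". Table 1, headed as the primary outcomes for Aims 1 and 2, treats the same three items as follows:

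- Enrollment: "≥70% of eligible enroll".
- Attendance: "≥70% session attendance".
- Retention: "≤20% participant attrition".

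Research Design and Methods gives the size of the study: "We plan to enroll approximately N=20 participants", in two groups of about 8, "accounting for 20% anticipated lost to follow-up".

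The Analysis Plan assesses the Aim 1 and Aim 2 outcomes descriptively. It also compares participants on demographic and clinical variables, including "those who enrolled and dropped out". It sets no retention threshold and does not say which of the two marks applies.

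**The concern.** An attrition ceiling of 20% is a retention floor of 80%. Aim 1 puts the floor at 70%. The other two items in the same hypothesis carry the same figure in both places, so the gap is specific to retention and is not a general difference between a summary and a detailed table.

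The primary outcomes are judged against fixed benchmarks and not by a hypothesis test, so the benchmark is the decision rule. If observed retention falls from 70% up to but not including 80%, the team could report the criterion as met (citing Aim 1) or not met (citing Table 1), and that choice would be made after the data are known.

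**Working it through.** **Inputs**

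- Aim 1 mark: retained/N ≥ 0.70 (Specific Aims).
- Table 1 mark: (N − retained)/N ≤ 0.20, that is, retained/N ≥ 0.80 (Measured Outcomes).
- N of about 20, two groups of about 8, 20% anticipated loss (Research Design and Methods).

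**The plan's own figure.** Two groups of 8 make 16. Inflating for 20% loss gives 16 / (1 − 0.20) = 20, which is the stated enrollment. The sample-size arithmetic is correct, and the problem lies only in the pass marks.

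**Cut-offs.** The smallest number retained that meets each mark:

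| N enrolled | Aim 1 (≥70% retained) | Table 1 (≤20% attrition) | Counts with opposite verdicts |
|---|---|---|---|
| 16 | 12 | 13 | 12 |
| 18 | 13 | 15 | 13, 14 |
| 20 | 14 | 16 | 14, 15 |
| 22 | 16 | 18 | 16, 17 |

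At N = 20, 14 retained is 70% (30% attrition) and 15 retained is 75% (25% attrition). Both meet Aim 1 and fail Table 1. Enrollment is stated as approximate, but the gap exists at every N shown.

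**Chance of a split verdict at the planned rate.** Let X be the number retained, with X ~ Binomial(20, 0.80), assuming participants drop out independently:

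- P(X = 14) = C(20,14) × 0.8^14 × 0.2^6 = 0.109
- P(X = 15) = C(20,15) × 0.8^15 × 0.2^5 = 0.175
- P(split) = 0.109 + 0.175 = 0.284
- P(pass under Aim 1) = P(X ≥ 14) = 0.913
- P(pass under Table 1) = P(X ≥ 16) = 0.630

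The two marks therefore agree in about 72% of cases (1 − 0.284 = 0.716).

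**Sensitivity.** The documents give only the 20% anticipated loss. The other true retention rates below are assumptions.

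| True retention | P(split), N = 18 | P(split), N = 20 | P(split), N = 22 |
|---|---|---|---|
| 0.70 | 0.370 | 0.371 | 0.330 |
| 0.75 | 0.412 | 0.371 | 0.376 |
| 0.80 | 0.366 | 0.284 | 0.324 |
| 0.85 | 0.238 | 0.148 | 0.189 |
| 0.90 | 0.092 | 0.041 | 0.058 |

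Participants are treated in two groups, so dropout may be correlated within a group. With two groups of 10, a beta-binomial count within each group and 80% retention, P(14 or 15 of 20) is 0.249, 0.222 and 0.184 at assumed intraclass correlations of 0.05, 0.10 and 0.20.

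**The case against.** The strongest reply is that precedence is fairly clear. Table 1 is titled as the primary outcomes and the text refers the reader to it for detail, while Aim 1 is a one-line summary. An ordinary reader would treat Table 1 as operative. That is a good reason to choose the Table 1 mark when the text is corrected. It does not remove the conflict, because Aim 1 is the stated hypothesis and the results could still be reported against it.

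A second reply is that the stakes are small. This is a single-arm pilot with a descriptive analysis, no stopping rule or go/no-go decision is tied to retention, and a reader given the count could apply either mark. This stands as a limit on weight: retention is one of many benchmarks in Table 1, and no rule combines them into an overall verdict.

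Third, the anticipated 20% loss is a planning assumption and not a success criterion. That is correct. It is consistent with the Table 1 figure, but only Table 1 states an 80% pass mark.

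Two textual escapes do not work. Reading 70% as belonging to attendance alone would leave enrollment and retention without a threshold in that hypothesis, although Table 1 gives enrollment the same 70%. Treating retention and attrition as separate measures fails because Table 1 places the attrition ceiling in its Retention row and no separate definition or denominator is given.

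**Conclusion.** The contradiction is real and lies in the current text: a primary feasibility criterion has two pass marks ten percentage points apart. With 20 enrolled, 14 or 15 retained gives opposite verdicts. The chance of that is 0.28 at the plan's own 80% retention with independent dropout, and 0.25 to 0.18 if dropout is correlated within groups at the assumed levels. At other assumed retention rates with N = 20 it runs from 0.37 (70% or 75% retained) down to 0.04 (90% retained). A split is thus a realistic outcome near the planned rate and unlikely if retention is very high.

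The consequence is confined to the retention criterion. It should be fixed, but it does not by itself undermine the trial.

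**What to change.** State one retention mark in both Specific Aims and Table 1. The natural choice is to reword Aim 1 hypothesis (1) as: enrollment ≥70%, attendance ≥70%, retention ≥80% (attrition ≤20%). Table 1 is the detailed outcome table, and its figure is consistent with the loss assumed in the sample size. If the team meant 70% as a minimum and 80% as a target, label them that way in both places.

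The cost is one line of text, and the Aim 1 hypothesis becomes stricter. If retention is exactly as planned, the chance of meeting it at N = 20 falls from 0.91 to 0.63, so the criterion would be missed about 37% of the time. The team should accept that knowingly. Keeping 70% and changing Table 1 to match would also remove the conflict, at the price of a looser primary benchmark.

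As a separate, minor addition while the row is being edited, give the denominator (all enrolled participants) and say which event, by which time point, counts as attrition. Research Design and Methods, Table 1 and the Analysis Plan use three different terms for loss and define none of them.

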**Exit interview:**

Upon completion of the intervention, participants will be asked to complete a 45-60 minute individual exit interview via phone or video conference. These interviews will be audio-recorded for transcription. The exit interview guide is included in the IRB submission.

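### Table 1 states no denominator for its acceptability marks and no plan to seek them from people who leave; at the loss the plan tolerates, a 75% pass among respondents is 60% to 80% of those enrolled.

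*Combined protocol and SAP*

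**What the plan says.** Measured Outcomes names feasibility and acceptability as the primary outcomes. In Table 1, intervention acceptability is a mean program satisfaction of at least 7.0, at least 70% intending to use the skills, and "≥70% would recommend the program to others", all taken from the post-survey. Likes, dislikes and suggestions come from the exit interview. The acceptability entries for surveys and actigraphy have the same two sources.

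On timing, Pre-post survey measures places the battery within about a week either side of the intervention. The Exit interview section says: "Upon completion of the intervention, participants will be asked to complete a 45-60 minute individual exit interview".

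The same table tolerates loss. Retention is met at "≤20% participant attrition", and the survey mark is "≥70% pre-intervention and post-intervention surveys completed".

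For Aims 1 and 2 the Analysis Plan specifies proportions, means or medians, and their spread. It names no analysis set and no rule for a missing acceptability answer. Its missing-data sentence (maximum likelihood, with last observation carried forward as a sensitivity analysis) stands in the Aim 3 paragraph. Dropouts are to be compared on demographic and clinical variables only. The safety text in Research Design and Methods says that people who withdraw need not give a reason.

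**The concern.** A person who stops the program is the one least likely to return an end-of-program survey or sit for an exit interview. If some of those people stop because the program did not suit them, a percentage or mean over respondents overstates how acceptable it was to those who were offered it. The safety text itself foresees program-related reasons: it plans for significant distress after the first session, and gives people with worsening symptoms the option to exit. Others will leave for unrelated reasons, and the plan has no means of telling the two apart.

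Two things are at stake. With about 20 people, the unstated denominator can decide whether a 70% mark on a primary outcome is met. The first group's experience is also used to refine the program for the second group, and the views of people who stopped are useful for that.

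**Working it through.** **Inputs from the documents**
- Research Design and Methods: "We plan to enroll approximately N=20 participants"; "approx. n=8 survivors/group, accounting for 20% anticipated lost to follow-up"; "We will hold two intervention cohort groups that will be run sequentially".
- Table 1: attrition of at most 20%, survey completion of at least 70%, acceptability proportions of at least 70%, mean satisfaction of at least 7.0.

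**Assumptions:** exactly 20 enrol; the 70% survey mark is taken over those 20; satisfaction is scored 1 to 10 (Table 1 gives that range for the ease and interference items, not for satisfaction).

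**The plan's own figure.** Two groups of 8 retained is 16, and 16 / (1 − 0.20) = 20. The stated enrolment reproduces, and the planned loss is 20 − 16 = 4 people.

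**Proportion marks.** With r endorsing among n respondents, the respondent figure is r/n. Over all 20 the worst case is r/20 (no non-responder endorses) and the best case is (r + 20 − n)/20 (all do). Taking the smallest r that passes among respondents:

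| Respondents | Smallest pass | Worst case of 20 | Best case of 20 |
|---|---|---|---|
| 16 (20% loss) | 12/16 = 75% | 12/20 = 60% | 16/20 = 80% |
| 14 (70% return) | 10/14 = 71.4% | 10/20 = 50% | 16/20 = 80% |

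In the first row attrition is 4/20 = 20% (met), survey return is 16/20 = 80% (met) and recommendation is 75% (met), yet only 60% of those enrolled are known to recommend the program.

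**How far off the respondent figure could be.** With 20% leaving, stayers endorsing at rate s and leavers at rate l, the excess is s − (0.8s + 0.2l) = 0.2(s − l). For s = 75%:
- l = 0%: 15 points
- l = 25%: 10 points
- l = 50%: 5 points
- l = 75%: 0 points

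The values of l are illustrative; the documents give none.

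**When the worst case still passes.** It needs 14 of 20: 14/16 = 87.5% of respondents at 20% loss, or 14/14 = 100% at 70% return.

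**Enrolled versus started.** People who leave before session 1 have no program to rate. With 16 respondents and 12 endorsing:
- None of the 4 leaves before session 1: 12/20 = 60% to 16/20 = 80%.
- Two do: 12/18 = 67% to 14/18 = 78%.
- All four do: 12/16 = 75%, with nobody unknown.

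**Mean mark.** With a respondent mean of 7.0 and non-responders averaging x, the overall mean is (7.0n + (20 − n)x)/20:

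| x | n = 16 | n = 14 |
|---|---|---|
| 1 | 5.8 | 5.2 |
| 4 | 6.4 | 6.1 |
| 7 | 7.0 | 7.0 |
| 10 | 7.6 | 7.9 |

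A respondent mean of 7.5 with n = 16 falls below 7.0 overall only if the other four average under 5.0, since 16 × 7.5 + 4x < 140 gives x < 5.0.

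**The case against.** A reader might infer that the plan takes acceptability only from people who finish. The documents do not say so. The post-survey is tied to a point in time, and the remuneration text pays $10 separately for it and for the exit interview, with no attendance condition. Someone who stops attending without withdrawing could therefore still be surveyed. The interview wording can also be read as timing, not as a condition. This stands: the gap is silence about leavers, not a rule that excludes them.

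A reader might also infer that the result is biased upward. That is plausible in direction but not established. The excess is zero if leavers resemble stayers, and both best cases above reach 80%. The 60% and 50% figures are worst cases, not estimates.

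Loss is not hidden either. Retention, attendance and survey completion are primary marks in the same table, and heavy loss would show as a failed mark. But the worked case meets both the retention and the survey marks, and nothing links the loss to the acceptability result.

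Other channels exist. The daily diary carries a few acceptability items, participants can ask for an individual check-in, and weekly meetings review difficulties. The diary items concern the diary, not the program, and the rest is informal.

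Finally, counting every non-responder as a rejection folds retention into acceptability and can require 87.5% or 100% endorsement among respondents. That stands, and it is why the worst case belongs beside the respondent figure and should not replace it.

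**Conclusion.** The concern holds as a gap in definition and follow-up. The acceptability marks rest on end-of-program instruments, with no stated denominator, no rule for missing answers and no plan to approach leavers. Reading the Aim 3 missing-data sentence across would not settle it, because there is no meaningful rating from before the program to carry forward.

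At 20% loss, the smallest pass among 16 respondents (75%) is compatible with 60% to 80% of 20 enrolled. At 70% survey return, 71% among 14 is compatible with 50% to 80%. Both ranges straddle 70%, so the handling of non-responders alone can decide the mark. The size of any bias is unknown.

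These figures rest on exactly 20 enrolled and on non-responders about whom nothing is known; the range over all who started is narrower if some leave before session 1. The means also assume a 1 to 10 satisfaction scale. For a descriptive open pilot this is a worthwhile, inexpensive improvement, not a defect that invalidates the study.

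**What to change.** - In the data collection text, add that everyone who attended at least one session, including anyone who stops, is offered the existing acceptability items and exit interview at the time they stop. Make it voluntary, in keeping with the rule that no reason for withdrawal is required.
- In Table 1 or the Analysis Plan, state the denominators. Report each 70% mark over respondents and over all who started, with best- and worst-case bounds for non-responders.
- State that a mark will not be described as robustly met when its bounds straddle 70%.
- For the mean satisfaction mark, give the respondent mean with a sensitivity range for non-responders, and state the scale.

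The cost is a few sentences, one extra voluntary contact for each person who stops, and a reported figure that may look less favorable. The instruments and payments already exist.
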